3.8.2.5 Duration of response

DoR applies only to patients whose best overall response was CR or PR. The start date is the date of first documented response (CR or PR, which must be confirmed subsequently) and the end date is the date of event defined as the first documented progression or death due to underlying cancer. The start date will be determined using the time the response was first determined and not using the time the response was confirmed. If a patient has not had an event, duration will be censored at the date of last adequate tumor assessment using the same censoring rule described for primary PFS analysis. DoR will be summarized by treatment arm. The distribution of duration of response will be estimated using the Kaplan-Meier method and the median response duration will be presented along with 95% confidence interval only if a sufficient number of responses are observed.

3.8.2.6 ECOG performance status

The ECOG PS scale ([Table 3-3](#)) will be used to assess physical health of patients, ranging from 0 (most active) to 5 (least active):

Table 3-3 ECOG Performance Scale

Score	Description
0	Fully active, able to carry on all pre-disease performance without restriction
1	Restricted in physically strenuous activity but ambulatory and able to carry out work of a light or sedentary nature, e.g., light house work, office work
2	Ambulatory and capable of all self-care but unable to carry out any work activities. Up and about more than 50% of waking hours
3	Capable of only limited self-care, confined to bed or chair more than 50% of waking hours
4	Completely disabled. Cannot carry on any self-care. Totally confined to bed or chair
5	Dead

The following intervals will be used to group the ECOG PS data over time. Day in columns 2 and 3 is defined as date of ECOG PS assessment date – randomization date + 1. The corresponding Day in column 1 assumes that a patient is treated on the day of randomization; however the definition of Day in columns 2 and 3 still applies if this is not the case, i.e. randomization date is taken as the reference for the windows.

Table 3-4 Time windows for ECOG PS assessments

Assessment	Target day of assessment	Time Interval
Baseline		Day 1 (if not available use screening)
Cycle 2 Day 1	29	Day 2 to day 42
Cycle k Day 1 (k≥3)	$d=(k-1)*28+1$	Day d-14 to day d+13
End of Treatment		Assessment taken at the end of treatment visit

If more than one assessment is done within the same time window, the assessment performed closest to the target date will be used. If 2 assessments within a time window are equidistant from the target date, then the worst of the 2 assessments will be used.

Frequency counts and percentages of patients in each score category will be provided by treatment arm and time point.

An analysis of time to definitive deterioration of performance status will be performed. The time to definitive deterioration is calculated from the date of randomization. Definitive deterioration is defined as an increase in ECOG PS by at least one category from the baseline score or death due to any cause. Deterioration is considered definitive if no return to baseline or better in ECOG PS is observed subsequent to the deterioration during the treatment period.

If a definitive deterioration is observed after two or more consecutive missing assessments, time to deterioration will be censored at the date of the last ECOG PS assessment prior to the deterioration. The number of missing assessments is calculated based on the time window in Table 3-4 and a rule similar for tumor assessments (see detail in section 2.5.5).

Patients receiving any further anti-neoplastic therapy before definitive deterioration will be censored at the date of their last assessment before the start date of the therapy. Patients that have not worsened as of the cutoff date will be censored at the date of their last assessment before the cutoff.

Kaplan-Meier estimates will be constructed for each treatment arm. The median, 25th and 75th percentiles for time to definitive deterioration for each treatment group will be obtained along with 95% confidence intervals.

A stratified log-rank test at one-sided 2.5% level of significance will be used to test the difference in time to definitive worsening of performance status between treatment arms. A (stratified) Cox proportional hazards model will be used to estimate the hazard ratio (with 95% confidence interval).

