Prior exposure to endocrine therapy subcategories included in groups A and B, were collated based on mPFS or TTP. Subcategory A grouped patients with PFS or TTP above 10 months (Paridaens et al. 2008; Mouridsen 2001; Robertson 2014; Finn 2015); whereas subcategory B grouped patients with shorter PFS or TTP around 4-6.5 months (Di Leo 2012; Dombernowsky 1998; Buzdar 1998; Johnston 2012).

Patients will be treated until disease progression, unacceptable toxicity, or discontinuation from the study treatment for any other reason (see Figure 4-1). PFS, as assessed by the local radiologists/investigators and using RECIST 1.1 criteria will be the primary endpoint. PFS as assessed through blinded independent central review will be used for supportive evidence of the primary efficacy endpoint.

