Patients who discontinue study treatment should NOT be considered withdrawn from the study. They should return for the assessments indicated in [Section 7.1.5](#) and [Section 7.1.6](#). If they fail to return for these assessments for unknown reasons, every effort (e.g. telephone, email, letter) should be made to contact them as specified in [Section 7.1.7](#). The patient remains on study until such time as he/she completes protocol criteria for ending study assessments. At that time, the reason for study completion should be recorded on the End of Post Treatment Phase Disposition CRF page.

Patients who discontinue study treatment should be scheduled for an End of Treatment (EOT) visit within 15 days following the date study treatment is permanently discontinued, at which

time all of the assessments listed for the EOT visit will be performed. For details of assessments, refer to [Table 7-1](#). If the decision to discontinue the patient occurs at a regularly scheduled visit, that visit may become the EOT visit rather than having the patient return for an additional visit.

An End of phase disposition eCRF page should be completed, giving the date and reason for stopping the study treatment. If a withdrawal occurs, or if the patient fails to return for visits, the investigator must determine the primary reason for a patient's premature withdrawal from the study and record this information on the EOT eCRF page. The EOT visit is not considered the end of the study.

At a minimum, all patients who discontinue study treatment, including those who refuse to return for a final visit, will be contacted for safety evaluations during the 30 days following the last dose of study treatment.

The investigator must also contact the IRT to register the patient's discontinuation from study treatment.

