### **10.5.2.5 ECOG performance status**

ECOG PS scale as described in [Section 7.2.2.4](#) will be used to assess physical health of patients. An analysis of time to definitive deterioration of the ECOG PS by one category of the score from baseline will be performed. Deterioration is considered definitive if no improvements in ECOG PS status is observed at a subsequent time of measurement during the treatment period following the time point where the deterioration is observed.

Patients receiving any further therapy prior to definitive worsening will be censored at their date of last assessment prior to start of therapy. Patients that have not worsened at the data cut-off point will be censored at the date of last assessment prior to start of therapy. Kaplan-Meier method will be used to estimate the distribution of time to definitive worsening and median time to definitive worsening will be presented along with a 95% confidence interval. A stratified log-rank test at one-sided 2.5% level of significance will be used to compare the distribution of time to definitive worsening between the 2 treatment arms.

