Analysis of the time to definitive 10% deterioration in the primary and the secondary PRO variables of interest will be performed. Definitive 10% deterioration is defined as a worsening in score by at least 10% compared to baseline, with no later improvement above this threshold observed during the treatment period, or death due to any cause. Time to deterioration is the number of days between the date of randomization and the date of the assessment at which deterioration is seen. If a patient has not had an event prior to analysis cut-off, start of new anti-neoplastic therapy, lost to follow-up, end of treatment or withdrawal of consent, the time to deterioration will be censored at the date of the last evaluation before the earliest of these times. Only assessments collected while the patient is on treatment and on or before the end of treatment visit will be included in the PRO time to deterioration analysis. If deterioration is observed after two or more missing assessments, time to deterioration will be censored at the date of the last assessment prior to the deterioration. The rules for calculating number of missing assessments are the same as those for tumor assessments (see details in Section 2.5.5). Time to 10% deterioration in the global health status/QOL scale, and secondary PRO scales of interest as listed above, will be compared between the two treatment arms using a

stratified log-rank test (strata based on IRT data) at 2 sided 5% level of significance. The survival distributions will be presented descriptively using Kaplan-Meier curves. Summary statistics from the Kaplan-Meier distributions will be determined, including the median time to 10% deterioration and the proportions of patients without 10% deterioration at 2 month intervals. Both point estimates and 95% CIs will be presented. A stratified Cox regression model will be used to estimate the hazard ratio (HR) of time to deterioration, along with 95% confidence interval. Sensitivity analysis of time to definitive deterioration with different cut-off definitions (e.g. 5%, 15%) may also be considered if the number of events per arm is judged sufficient to draw relevant conclusions.

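### The ECOG definitive-deterioration rule ties event status to length of treatment, so its one-sided 2.5% log-rank test leans towards ribociclib even if performance status is identical in both arms

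*SAP*

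**What the plan says.** The SAP for the primary PFS analysis, section 3.8.2.6, sets the event: "Definitive deterioration is defined as an increase in ECOG PS by at least one category from the baseline score or death due to any cause". It then says when a worsening is definitive: "Deterioration is considered definitive if no return to baseline or better in ECOG PS is observed subsequent to the deterioration during the treatment period". Protocol section 10.5.2.5 has the same look-ahead in different words: "Deterioration is considered definitive if no improvements in ECOG PS status is observed at a subsequent time of measurement during the treatment period". The two are not identical: the protocol asks for no improvement rather than no return to baseline, and does not name death as an event.

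The last ECOG window in SAP Table 3-4 is EOT: "Assessment taken at the end of treatment visit". Protocol section 7.1.3 has patients "scheduled for an End of Treatment (EOT) visit within 15 days following the date study treatment is permanently discontinued". Protocol Table 7-1a shows no performance-status assessment after that visit.

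On treatment length, protocol section 4.1 says: "Patients will be treated until disease progression, unacceptable toxicity, or discontinuation from the study treatment for any other reason". On the comparison, SAP 3.8.2.6 says: "A stratified log-rank test at one-sided 2.5% level of significance will be used to test the difference in time to definitive worsening".

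SAP 3.8.2.6 has two censoring rules. A deterioration seen after two or more consecutive missing assessments is censored. So is a patient who starts further anti-neoplastic therapy before definitive deterioration. Neither removes a worsening first recorded at an EOT visit that follows regular attendance and precedes new therapy. No sensitivity analysis addresses the rule.

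**The concern.** Whether a worsening is an event is decided by what is seen afterwards, and the looking stops when treatment stops. A one-category worsening at EOT, or at the last visit before cut-off, cannot be cancelled. The same worsening in a patient who stays on treatment disappears if a later visit is back at baseline.

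The chance that a given worsening counts therefore depends on how soon treatment ends, and the trial is designed to make that differ between arms. Placebo patients reach their last assessment sooner, so their uncancellable worsenings are dated sooner. A log-rank test reads that as slower deterioration on ribociclib. At stake is the stated 2.5% level of a named secondary endpoint, with a bias in one direction.

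SAP section 3.8.2.7 uses the same look-ahead for the 10% PRO deterioration endpoint: "with no later improvement above this threshold observed during the treatment period, or death due to any cause". There, questionnaires continue into efficacy follow-up but only those up to the EOT visit enter the analysis, so later scores that could show recovery are collected and left out.

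**Working it through.** **Plan's own figure.** No event count or power is stated for the ECOG endpoint, so I checked the planned PFS gap, which stands in for the treatment-time gap. Schoenfeld events for HR 0.67, one-sided 2.5%, 95% power, 2:1 allocation:

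(1.960 + 1.645)² / [(2/3)(1/3)(ln 0.67)²] = 12.995 / (0.2222 × 0.1604) ≈ 365, against 364 stated. Median on ribociclib: 9 / 0.67 = 13.4 months, as stated.

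**Mechanism in a limiting case.** Suppose every event is a transient worsening that happens to be present at the stop visit, with probability p in either arm. The event hazard is then p × the stopping hazard.
- Placebo: ln 2 / 9 = 0.0770 per month; with p = 10%, 0.0077.
- Ribociclib: ln 2 / 13.4 = 0.0517 per month; with p = 10%, 0.0052.

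The ratio is 0.67 with no difference in performance status. Events at the data cut-off and true deterioration common to both arms pull it back towards 1, so the full design was simulated.

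**Inputs from protocol section 10.8.** N = 660, 2:1; 40% first line and 60% second line; control medians 18 and 6.5 months; HR 0.67 for stopping; uniform accrual over 19 months; cut-off at month 26; dropout hazard 0.0105 (taken as per month). ECOG every 28 days plus an EOT visit within 15 days. Log-rank stratified by line, one-sided 2.5%. Simulated PFS events at month 26 were 356 (369 with a single 9-month control median), within 3% of 364.

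**Assumed, because the documents give no values.** Share of assessments showing a transient worsening (5-30%), spell length (1-3 cycles), and a permanent deterioration or death hazard common to both arms (0-0.02 per cycle). Performance status is identical in both arms and independent of stopping. The model has no missed visits and no new therapy.

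**Results for the rule as written** (10,000 trials per row, one-cycle spells):

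| Transient worsening | Permanent hazard per cycle | Stopping HR | Rejection | ECOG HR |
|---|---|---|---|---|
| 5% | 0.01 | 0.67 | 5.5% | 0.93 |
| 10% | 0.01 | 0.67 | 8.2% | 0.90 |
| 20% | 0.01 | 0.67 | 14.2% | 0.87 |
| 30% | 0 | 0.67 | 27.0% | 0.81 |
| 10% | 0.01 | 1.00 | 2.8% | 1.00 |

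A separate run gave 6.0%, 8.3% and 14.5% at 5%, 10% and 20%, and 2.2% with equal stop times. The last row of the table isolates treatment length as the cause. The whole grid with unequal stopping spans 4.5% to 27%.

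**Variants** (10% transient, two-cycle spells, hazard 0.01): base 7.3%; ECOG every third cycle 7.9%; N = 727 7.4%; cut-off at month 39 8.1%; stopping HR 0.8 5.7%; stopping HR 0.55 10.5%.

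**Where the signal sits** (10% row, unequal stopping): 18.6% of ribociclib and 17.3% of placebo patients have an event, but the rate per cycle at risk is 0.0186 against 0.0199.

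**Alternatives.** First worsening confirmed at the next assessment, dated at the confirming visit, later recovery ignored: 3.1-4.1% across the main grid and 5.4-5.6% with ECOG every third cycle (2.7-3.8% and 3.3% in the separate run). Keeping the present rule and only requiring at least one later on-treatment visit: 3.5-15%.

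**The case against.** The strongest objection concerns the null. Patients are treated until progression, so a worsening recorded at EOT may well be real and caused by progression. Its later arrival on ribociclib would then be a treatment effect, and the endpoint is openly an on-treatment one. This stands in part: the rejection rates above assume that performance status is independent of stopping. It does not rescue the rule, which counts a passing fluctuation at the last visit exactly as it counts a true decline.

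Second, the size rests on assumed fluctuation rates, and PFS is only a proxy for time on treatment; stops for toxicity on ribociclib would narrow the gap. Both points stand. With a stopping HR of 0.8 the rate is 5.7%, lower but still above nominal.

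Third, the consequence is limited. The objective is to evaluate rather than compare, the hierarchical strategy covers only PFS and OS, and the documents tie no claim to the ECOG test. This stands too.

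A reader might infer that placebo patients have more events. They do not: the share is about equal, or slightly higher on ribociclib. A reader might also carry these figures over to the PRO endpoint. Its schedule, threshold and two-sided 5% test differ, protocol section 10.5.5 says PRO data will have no formal tests, and no magnitude has been computed.

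**Conclusion.** The concern holds as a bias of known direction and assumption-dependent size. A worsening at the last on-treatment assessment counts while the same worsening earlier can be cancelled. With planned median PFS of 9 and 13.4 months as the guide to treatment length, placebo events come earlier and at a higher rate per time at risk.

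With identical performance status independent of stopping, and transient worsening at 5-20% of assessments, the one-sided 2.5% test rejects about 5-15% of the time, roughly two to six times nominal. With equal treatment duration it rejects about 2-3%. The 27% figure belongs to an extreme setting (30% transient worsening, no permanent deterioration) and should not be read as typical.

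Nor do the documents support the inference that a significant ECOG result would be wholly artefact. To the extent that performance status worsens with progression, part of a difference is real. The fault is that the present rule cannot tell the two parts apart. PFS and OS conclusions are untouched.

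**What to change.** In SAP section 3.8.2.6:

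1. Keep the Kaplan-Meier and hazard-ratio display of time to definitive deterioration, and label its log-rank p-value as nominal.
2. Add a sensitivity analysis. The event is the first worsening of at least one category confirmed at the next assessment, or death. It is dated at the confirming visit or at death. Later recovery does not cancel it. Patients without confirmation are censored at their last assessment.
3. State that a performance-status benefit is claimed only if this analysis agrees.
4. Reconcile the ECOG schedule so that the next assessment is defined. The protocol summary and SAP Table 3-4 work by cycle; protocol Table 7-1a, headed as the schedule after Amendment 4, shows every third cycle after Cycle 3. On that schedule two Table 3-4 windows lie empty between visits, so the two-missing-assessments rule needs the same attention. Align the protocol and SAP definitions as well.

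Only requiring some later assessment under the present rule is not enough, since it leaves 3.5-15%.

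For the PRO endpoint in section 3.8.2.7, note that the same look-ahead applies and that questionnaires after EOT are collected but excluded.

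The cost is SAP wording and one derivation on data already collected. A worsening first seen at EOT is not counted unless death follows. Some power is lost; the amount was not computed for this definition. A small inflation remains, about 3-4%, or up to about 5.6% with every-third-cycle visits, because the off-schedule EOT visit comes earlier on placebo.

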3.8.2.7 Patient reported outcomes

The European Organization for Research and Treatment of Cancer's core quality of life questionnaire (EORTC-QLQ-C30, version 3.0) and the EuroQoL 5-level instrument (EQ-5D-5L, Version 4.0) will be used to evaluate patient-reported outcome measures of health-related quality-of-life, functioning, disease symptoms and treatment-related side effects. The BPI-SF will be used to assess patient's subjective assessment of pain.

The PRO instruments are planned to be administered during screening and every 8 weeks after randomization in the first 18 months, and every 12 weeks thereafter until the end of treatment. PRO assessments will continue to be collected during the efficacy follow-up after the end of treatment.

The following time based intervals will be used to group the PRO data over time. Day is defined as date of PRO assessment date – randomization date + 1.

Table 3-5 Time windows for patient reported outcomes

	Time Interval
Baseline	Screening assessment
Cycle 3, 5, 7, 9 until cycle 19 Day 1	+/- 4 weeks centered around the planned assessment date (except for the first window and the last window): i.e. days (1, 85] for Day 1 of cycle 3 (2 th assessment) days (85, 141] for Day 1 of cycle 5 (3 th assessment) days (k*56-27; k*56+29] for (k+1 th assessment) days (477, 547] for 10 th assessment on Day 1 cycle 19
Cycle 22, 25, 28, ... Day 1	+/- 6 weeks centered around the planned assessment date: i.e. days (547, 631] for 11 th assessment days (631, 715] for 12 th assessment days (715, 799] for 13 th assessment
End of treatment	Assessment taken at the end of treatment visit
Efficacy follow-up	At each of the efficacy follow-up visits

If more than one assessment is done within the same time window, the assessment performed closest to the target date will be used. If 2 assessments within a time window are equidistant from the target date, then the assessment obtained prior to target date will be used. If the closest assessment to the target date has two questionnaires filled out on the same date, then the worst score of these assessments will be used for each subscale score.

The FAS will be used for all PRO summaries and listings.

The global health status/global QoL scale score of the EORTC QLQ-C30 is identified as a primary PRO variable of interest. The physical functioning, emotional functioning and social functioning sub-scale scores of the EORTC QLQ-C30, the visual analog scale (VAS) of the EQ-5D-5L, and worst pain item (based on question 3), pain severity index, and pain interference indices of the BPI-SF are identified as secondary PRO variables of interest. High scores in the EORTC QLQ-C30 represent a higher response level. Thus a high score for a functional scale represents a high / healthy level of functioning; a high score for the global health status / QoL represents a high QoL, but a high score for a symptom scale / item represents a high level of symptomatology /problems. Higher scores in the EQ-5D-5L also correspond to better health states. A higher score in BPI-SF corresponds to more pain.

The number of patients completing PRO questionnaires and the number of patients missing/expected to have PRO assessments will be summarized by treatment arm for scheduled assessment time points (the number of ongoing patients will be used as

denominator). Furthermore, the amount and the pattern of missing data may be explored by treatment arm and over time using summary statistics. The following categories will be used to describe whether the questionnaire was completed at a specific time point:

- yes, fully completed
- yes, partly completed
- no.

Scoring of raw data and methods for handling missing items or missing assessments will be handled according to scoring manuals for each respective patient questionnaire (Fayers 2001; Oemar and Janssen 2013; Cleeland 2009).

As the main analysis and to best utilize the repeated PRO assessments, a repeated measures model for longitudinal data will be used to compare the two treatment arms in sub-scales obtained from EORTC QLQ-C30 and the VAS score of EQ-5D-5L over time. This longitudinal model will include terms for treatment, the randomization stratification factors, time (duration in weeks counting from the time of baseline measurement to the time of a particular post baseline measurement), baseline value as main effects, and an interaction term for treatment by time. Time will be considered as a continuous variable in this analysis. As a first approach, an unstructured correlation matrix will be used to model the correlation within patients. The structure of the correlation matrix will be investigated and simplified using likelihood ratio tests if appropriate. Time is considered as a continuous variable in the analysis. The data for selected time points will be fitted using a linear model using treatment, stratification factors, baseline value as covariates. The differences in least square means between the experimental and control group, and the corresponding 2-sided 95% CI at selected time points will be presented.

For the mixed effects model, patients with baseline and at least one non-missing post-baseline assessments will be included. This analysis will only include assessments up to the time point where there are at least 50 patients on each of the treatments. Data collected up to EOT assessment will be included.

Analysis of the time to definitive 10% deterioration in the primary and the secondary PRO variables of interest will be performed. Definitive 10% deterioration is defined as a worsening in score by at least 10% compared to baseline, with no later improvement above this threshold observed during the treatment period, or death due to any cause. Time to deterioration is the number of days between the date of randomization and the date of the assessment at which deterioration is seen. If a patient has not had an event prior to analysis cut-off, start of new anti-neoplastic therapy, lost to follow-up, end of treatment or withdrawal of consent, the time to deterioration will be censored at the date of the last evaluation before the earliest of these times. Only assessments collected while the patient is on treatment and on or before the end of treatment visit will be included in the PRO time to deterioration analysis. If deterioration is observed after two or more missing assessments, time to deterioration will be censored at the date of the last assessment prior to the deterioration. The rules for calculating number of missing assessments are the same as those for tumor assessments (see details in Section 2.5.5). Time to 10% deterioration in the global health status/QOL scale, and secondary PRO scales of interest as listed above, will be compared between the two treatment arms using a

stratified log-rank test (strata based on IRT data) at 2 sided 5% level of significance. The survival distributions will be presented descriptively using Kaplan-Meier curves. Summary statistics from the Kaplan-Meier distributions will be determined, including the median time to 10% deterioration and the proportions of patients without 10% deterioration at 2 month intervals. Both point estimates and 95% CIs will be presented. A stratified Cox regression model will be used to estimate the hazard ratio (HR) of time to deterioration, along with 95% confidence interval. Sensitivity analysis of time to definitive deterioration with different cut-off definitions (e.g. 5%, 15%) may also be considered if the number of events per arm is judged sufficient to draw relevant conclusions.

Descriptive statistics (n, mean, median, SD, min, max) will be used to summarize the individual item and subscale scores from the EORTC QLQ-C30, EQ-5D-5L, and worst pain item (question 3), pain severity index and pain interference indices of the BPI-SF at each scheduled assessment time point. Additionally, change from baseline in the subscale scores at the time of each assessment will be summarized. Patients with an evaluable baseline score and at least one evaluable post baseline score during the treatment period will be included in the change from baseline analyses.

